AA can cause tremendous emotional and psychosocial distress in affected patients and their families [16]. There is a lack of effective treatments for patients with AA, with no universally proven therapy that induces and sustains remission and there is no cure [3]. Topical treatments are minimally effective, probably because of limited penetration. Nor is there robust evidence for efficacy of topical tacrolimus, cryotherapy or ultraviolet light A combined with oral psoralens (PUVA). Intralesional injections of corticosteroids are effective but can only be considered for patients with limited involvement. For more extensive alopecia forms, including AT or AU, for which spontaneous regrowth is rare, systemic immunosuppressants (systemic corticosteroids, cyclosporine A, mycophenolate mofetil, azathioprine, and Janus kinase inhibitors) have shown some efficacy but are associated with side effects that preclude long-term use [5, 17, 18]. Furthermore, hair loss recurs usually after treatment cessation [19]. Despite the multiple side effects associated with these treatments, these are still widely used due to the absence of other treatment options [3, 6].

[figure not shown]
TREATMENT RATIONALE:

The current systemic treatments for severe AA are broad acting, and therefore bear many adverse effects. Moreover, none of these therapies show effective, long lasting results [20]. Many patients, especially those with extensive involvement such as AT and AU, are willing to risk significant adverse drug effects and attempt off-label use of various treatments, including JAK kinase inhibitors which carry a black box warning due to potential serious infections and increased malignancies [18, 21]. There is an unmet need for targeted therapeutic strategies for patients with severe AA, similarly to the new effective treatment approaches that are now used or tested for other immune mediated diseases such as psoriasis and atopic dermatitis (AD) [22-25]. New biological treatments approved or in development for inflammatory skin conditions, such as AD, rely on targeting specific activated cytokine pathways. This revolutionary approach leads to a change in treatment paradigms for these diseases, with development of highly efficacious and safer therapeutics.

[figure not shown]

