- 7) Active hepatitis B, hepatitis C, human immunodeficiency virus (HIV), or positive HIV serology at the time of screening for subjects determined by the investigators to be at high-risk for this disease.
- 8) Subject has a suspected or active lymphoproliferative disorder or malignancy; OR a history of malignancy within 5 years before the Baseline assessment, except for completely treated in situ non-melanoma skin and cervical cancers without evidence of metastasis.
- 9) Subject has received a live attenuated vaccine \leq 30 days prior to study randomization.
- 10) Subject has any uncertain or clinically significant laboratory abnormalities that may affect interpretation of study data or endpoints.
- 11) Subject has any other medical or psychological condition that, in the opinion of the investigator, may present additional unreasonable risks as a result of their participation in the study and/or interfere with clinic visits and necessary study assessments.

- 12) History of adverse systemic or allergic reactions to any component of the study drug.
- 13) Severe, untreated asthma or a history of life-threatening asthma exacerbations while on appropriate anti-asthmatic medications.
- 14) Use of systemic immunosuppressive medications, including, but not limited to, cyclosporine, systemic or intralesional corticosteroids, mycophenolate mofetil, azathioprine, methotrexate, tacrolimus, or ultraviolet (UV) phototherapy with/without Psoralen Ultraviolet A (PUVA) therapy within 4 weeks prior to randomization.
- 15) Use of an oral JAK inhibitor (tofacitinib, ruxolitinib) within 12 weeks prior to the Baseline visit.
- 16) Subject has used topical corticosteroids, and/or tacrolimus, and/or pimecrolimus within 1 week before the Baseline visit.
- 17) Subject has been previously treated with dupilumab.
- 18) Subject currently uses or plans to use anti-retroviral therapy at any time during the study.

POTENTIAL RISKS OF DUPILUMAB:

Dupilumab showed good safety based on early and late phases in AD and asthma [37, 39-42]. Based on the nature of dupilumab, its mechanism of action, data from human and animal studies, and what is known about other similar drugs, possible risks include:

- Infections, including those caused by parasites (e.g. intestinal worms).

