- Injection site reactions: Injection site reactions observed in dupilumab clinical trials have been generally mild to moderate and resolved without requiring any treatment. Occasionally, such reaction may be severe and last more than 24 hours.
- Hypersensitivity/allergic reactions.
- Adverse consequences of forming antibodies to dupilumab
- Cancer: A potential risk for medications interfering with the immune system.
- Potential for interactions with other medications: It is not known if dupilumab may increase or decrease the effect of other medications.
- Inflammation of the eye: a potential risk of conjunctivitis has been reported.

PRIOR TREATMENT:

All relevant treatment received by the subject within 30 days before screening will be recorded. Over-the-counter drugs (e.g. vitamins, acetaminophen) taken by the subject within 14 days before screening will also be recorded.

CONCOMITANT TREATMENT:

Concomitant medications are permitted for the treatment of stable, chronic illness. Use of such concomitant medication or other medications that may be required throughout the study will be recorded (including the reason for treatment and name, dose, unit, route, and the date of treatment as appropriate) until week 72 or Early Termination.

At Week 48, if subjects want to seek other treatment options (including commercially available dupilumab) for AA, they may do so through their own dermatologist/physician. If a subject initiates a new treatment or obtains commercially available dupilumab at Week 48, then that treatment must be documented as a concomitant medication.

PROHIBITED TREATMENT:

All treatments prohibited during the screening period are also prohibited throughout the course of the study. No live attenuated vaccinations are permitted through the study. All subjects treated previously with dupilumab will be excluded from the study as above.

PROCEDURES:

Monitoring of AEs will begin at signing of the informed consent form and will be continued throughout the study. All study procedures will be completed at designated times during the study (see **Table 1**).

Trained assessors will perform clinical assessments. It is suggested that the same assessor/s perform these assessments for a subject.

Visit 1 – Screening (within 4 weeks of Baseline)*

- Sign and date an IRB-approved consent and HIPPA agreement
- Review Inclusion and Exclusion Criteria

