- Collect blood sample for mechanistic endpoints
- AA Clinical assessments (SALT, aaPGA, and eyebrow/eyelash)
- AD Clinical assessments, if applicable (EASI, IGA, SCORAD)
- Questionnaires (AASIS and AA-QLI)
- Standardized Photographs
- Perform biopsy of lesional skin of the scalp
- Perform a biopsy of lesional skin for subjects with a concomitant history of atopic dermatitis and an active AD lesion if present
- Record all changes in medications and adverse events

Considering there is no current treatment that is very effective in treating alopecia areata, these subjects are highly motivated to participate in a study that provides a treatment option.

TOTAL VOLUME OF BLOOD COLLECTED DURING THE STUDY:

Visit	Blood volume (mL)					
	1	2	5	8	11	14
Week	Screen	0	12	24	36	48
Serum HCG (where applicable)	10	n/a	n/a	n/a	n/a	n/a
HIV	10	n/a	n/a	n/a	n/a	n/a
HBV, HCV	10	n/a	n/a	n/a	n/a	n/a
CBC with diff	4	4	4	4	4	4
CMP, CRP, LDH	10	10	10	10	10	10
Total Serum IgE	10	10	10	10	10	10
Mechanistic studies	n/a	10	10	10	10	10
Total volume	54	34	34	34	34	34

The total estimated blood volume is 224 mL. Additional volumes may be required for repeat testing or as part of unscheduled visits.

DISCONTINUATION OF TREATMENT AND WITHDRAWAL OF SUBJECTS:

The reasons why a subject may discontinue or be withdrawn from the study include, but are not limited to the following: subject request, protocol violation, loss to follow up, subject non-compliance, study termination by investigators, and a confirmed grade 3 or higher adverse event, which is suspected to be related to test article administration. Subjects that elect to withdraw from the trial due to lack of efficacy and/or exacerbation of disease will undergo the following: vitals; urine pregnancy test (if applicable); lesional biopsy of the scalp (if withdrawing before the Week 24 visit); lesional biopsy of the AD lesion (if applicable, and if withdrawing prior to the Week 24 visit); blood evaluations (CBC, CMP, LDH, CRP, Total serum IgE, and blood sample for mechanistic endpoints); clinical evaluation (SALT, SCORAD, EASI, aaPGA, and eyebrow/eyelash scores); subject evaluations (AASIS and AAQLI); and photographs.

Stopping Rules

Patients will be permanently discontinued from study treatment in the event of:

- Anaphylactic reaction or other severe systemic reaction to study drug injection
- Diagnosis of a malignancy during study, excluding carcinoma in situ of the cervix, or squamous or basal cell carcinoma of the skin

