- Evidence of pregnancy
- Any infection that is opportunistic, such as active TB and other infections whose nature or course may suggest an immuno-compromised status
- Severe laboratory abnormalities:
 - Neutrophil count $\leq 0.5 \times 10^3/\mu\text{L}$
 - Platelet count $\leq 50 \times 10^3/\mu\text{L}$

- Alanine aminotransferase (ALT) and/or aspartate aminotransferase (AST) values >3x upper limit of normal (ULN) with total bilirubin >2x ULN (unless elevated bilirubin is related to confirmed Gilbert's Syndrome)
- Confirmed AST and/or ALT >5 x ULN (for more than 2 weeks)
- Treatment with any prohibited concomitant medication or procedure
- Other reasons that may lead to the permanent discontinuation of study drug include certain AEs deemed related to the study drug.

Study drug dosing may be temporarily suspended in the event of:

- Clinically important laboratory abnormalities, such as:
 - Neutrophil count $\leq 1.0 \times 10^3/\mu\text{L}$ but $>0.5 \times 10^3/\mu\text{L}$
 - Platelet count $\leq 100 \times 10^3/\mu\text{L}$ but $>50 \times 10^3/\mu\text{L}$
 - Creatine phosphokinase (CPK) >10x ULN
- Other intercurrent illnesses or major surgery
- An infection that requires systemic treatment with antibiotic, antifungal, antiviral, anti-parasitic, or anti-protozoal agents or requires oral treatment with such agents for longer than 2 weeks
- Treatment with systemic corticosteroids or non-steroidal immunosuppressive/immunomodulating medications (eg, cyclosporine, methotrexate, azathioprine, mycophenolate-mofetil, Janus kinase inhibitors, biologic agents, etc).

Duration of study drug suspension should be reviewed on a case by case basis and can be discussed among the PIs.

Unblinding

In case of an emergency, when knowledge of the test article assignment is required for the medical management of an individual subject, the subject will be unblinded. The code should be broken only in the event of a medical emergency, when knowing the treatment assignment is absolutely necessary. The investigators will notify the IRB, FDA and any other regulatory group, within 24 hours after determining that it is necessary to unblind the treatment assignment. The investigator must also indicate in source documents and in the CRF that the blind was broken and provide the date, time, and reason for breaking the blind. Any AE or SAE associated with breaking the blind must be recorded and reported as specified in this protocol.

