Matching placebo prefilled syringes (that will appear identical to the dupilumab syringes) will be provided by the company to the study sites. The subjects and the staff will remain unaware of the individual treatment assignment during the study. All study medication will be stored in a secure cool area between 2-8°C. Study drug will be administered to subjects at each study visit, with subsequent weekly injections performed by the patients at home. Patients (and/or caregivers) who are willing and able to administer dupilumab outside of the clinic will be trained on injecting study drug during the initial clinic visit.

We will query the subjects during each study visit on any missed injections and document this information. The investigative sites will account for all study drug dispensed and stored during the study.

STATISTICAL CONSIDERATIONS:

Sample Size Calculation

The primary outcome for this study is the SALT change at week 24. For patients with similar disease severity, a change in SALT of less than 5 units was observed ([name] et al, 2019). Assuming that dupilumab will induce a change in SALT of at least 25 units with a standard deviation of 10 at week 24, a sample size of 54 completed patients randomized 2:1 treatment to placebo (i.e. 36 in the treatment arm, 18 in the placebo arm) will provide 97% power to detect differences with Placebo based on a two-sided Student's t-test with a 0.05 type I error. Assuming that 10% of patients drop out of the study, we plan to enroll 60 total patients (i.e. 36 in the treatment arm, 18 in the placebo arm).

Demographics and Other Baseline Characteristics

Descriptive statistics of demographics and other baseline characteristics will be presented for all subjects and tabulated by treatment group. Presentations of age, sex, ethnicity, race and baseline will also be given. Other baseline characteristics include height, weight, and vital signs, duration of the AA and AD, concurrent diagnoses from medical history and indications for concomitant medication, concomitant medication, and previous AA and AD treatments.

Analysis of Primary Endpoint

A Mixed effect Model Repeated Measurement (MMRM) will be used to detect any overall differences in the treatment effect at week 24 compared to baseline.

Analysis of Secondary Endpoints

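### Stopping study drug is not separated from leaving the study, and no Week 24 SALT is provided for once drug is stopped

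*Combined protocol and SAP*

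**What the plan says.** Under Discontinuation of Treatment and Withdrawal of Subjects, a single sentence covers subjects who discontinue and subjects who are withdrawn from the study. The reasons given are "subject request, protocol violation, loss to follow up, subject non-compliance, study termination by investigators, and a confirmed grade 3 or higher adverse event", where the adverse event must be suspected to be related to the test article. The list is permissive and open-ended. The same paragraph sets out exit assessments for subjects who leave because of lack of efficacy or worsening disease.

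The Stopping Rules that follow are worded differently. They end study treatment permanently, and one trigger is "Treatment with any prohibited concomitant medication or procedure". Under Prohibited Treatment, "All treatments prohibited during the screening period are also prohibited throughout the course of the study". This carries forward exclusion criterion 16: "Subject has used topical corticosteroids, and/or tacrolimus, and/or pimecrolimus within 1 week before the Baseline visit". The Stopping Rules do not mention visits after drug is stopped.

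Study Withdrawal and the Early Termination column of Table 1 describe one exit visit, which includes SALT. Otherwise SALT is scheduled every 4 weeks to Week 24.

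Analysis of Primary Endpoint is one sentence naming an MMRM for Week 24 against baseline. It gives no analysis set, no rule for SALT after drug is stopped or after prohibited treatment, no missing-data assumption and no sensitivity analysis. The only remark on drop-out bias concerns secondary endpoints, where the mixed model is preferred to a completers-only analysis.

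**The concern.** The primary question is the difference in SALT change at Week 24 between the groups as randomised. Randomisation protects that comparison only if the Week 24 value is sought from everyone. Non-compliance, protocol violation, a related adverse event and disappointment with the result all arise after randomisation and can depend on the arm. If such patients leave with no Week 24 measurement, those still observed are a selected group in each arm.

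An MMRM deals with this only under missing at random: given a patient's observed SALT values, the unobserved Week 24 value must behave like that of similar patients who stayed. For a patient who has stopped drug, those similar patients are mostly still on drug. Without off-drug measurements the assumption cannot be checked.

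**Working it through.** **Inputs**
- Dupilumab change, from Sample Size Calculation: "Assuming that dupilumab will induce a change in SALT of at least 25 units with a standard deviation of 10 at week 24".
- Placebo change, same section: less than 5 units. Taking 5, the planned difference is 25 − 5 = 20.
- 54 completers (36 and 18), 10% drop-out, 60 enrolled. Investigational Drug Supply gives 40 and 20 as the randomised arms.
- About 20 of the 60 have atopic dermatitis (AD) or a history of it (Study Design Overview).
- The documents give no stopping rate by arm or by AD status.

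**Step 1. The plan's own figures.** Drop-out: 54 / (1 − 0.10) = 60, which reproduces, so 60 − 54 = 6 losses are expected. Power: the plan says its sample "will provide 97% power to detect differences with Placebo" using a "two-sided Student's t-test with a 0.05 type I error". With difference 20, SD 10 and 36 against 18, the noncentrality is 20 / (10 × √(1/36 + 1/18)) = 6.93 and power exceeds 99.99%. The 97% does not reproduce; it would need an SD of about 17.7. That is a separate matter and does not decide this point.

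**Step 2. What the text provides for each kind of early stopper**
- *Non-compliance, protocol violation, related grade 3 or higher event:* may discontinue or be withdrawn from the study. If withdrawn, an exit visit with SALT; no Week 24 SALT.
- *Prohibited treatment or a safety stopping rule:* study treatment ends. Whether the patient stays in the study is not addressed, and no later visit is described.
- *Subject's own request or lack of efficacy:* exit visit with SALT; no Week 24 SALT.

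In no case is a site told to obtain Week 24 SALT from a patient off drug.

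**Step 3. Bounding case, dupilumab arm.** Suppose a fraction f of dupilumab patients stop, return fully to the placebo level by Week 24, and are credited with the on-drug mean. The overstatement is f × (25 − 5). At f = 10%, 0.10 × 20 = 2 units. This is an upper bound at that stopping rate, provided stoppers end no worse than placebo. An MMRM conditioning on a poor responder's earlier and exit SALT would not credit the full 25 units.

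**Step 4. Illustration, placebo arm.** If k of 20 placebo patients are unobserved and their true Week 24 change differs by D units from that of the patients retained, the completers' mean is shifted by (k / 20) × D. D is assumed to lie between 5 and 20.
- k = 2: 0.5 to 2.0 units.
- k = 6 (all expected losses on placebo, an extreme case): 1.5 to 6.0 units.

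An MMRM would recover part of this if data are missing at random.

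**Step 5. Direction.** If placebo patients who do badly leave, the remaining placebo patients look better and the treatment difference shrinks. If dupilumab patients who do badly leave, it grows. The net sign is unknown.

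**Step 6. Precision.** With all six losses on placebo (40 against 14) and a difference of 20, power is above 99.9% at SD 10, 95.1% at SD 17.5 and 88.5% at SD 20. The corresponding figures for 36 against 18 are above 99.9%, 97.3% and 92.5%. Under the plan's SD the issue is bias, not power.

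**The case against.** The strongest defence is that the text does not order anyone out. The withdrawal sentence is permissive, prohibited treatment ends study treatment only, and the exit procedures are triggered by leaving the study, not by stopping drug. SALT is measured every 4 weeks and at exit, so most information on an early stopper can enter the MMRM. Patients are described as strongly motivated, and all receive dupilumab from Week 24, which favours retention on placebo.

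Most of this stands, and it rules out several stronger readings:
- *Every patient who stops drug is removed from the study.* The documents do not say so. For the Stopping Rules, what follows is a gap in the text.
- *The losses will mainly be atopic placebo patients needing a banned topical agent.* One third of 20 placebo patients is 6 to 7, and the mechanism is plausible, but the documents do not state it. The AD group includes patients with only a history of AD. The 38.2% in the background is atopy in general, including rhinitis and asthma.
- *The protocol itself expects regrowth on dupilumab to be lost on stopping.* The statement that "hair loss recurs usually after treatment cessation" follows a sentence on other systemic immunosuppressants and cites a study of cyclosporine with PUVA. Extending it to dupilumab is an assumption.
- *30% of the placebo arm will be unobserved.* That is 6/20, with every expected loss on placebo.

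The defence does not supply a Week 24 value for patients off drug, nor prevent withdrawal from the study for non-compliance or protocol violation. Motivation suggests that off-drug attendance is feasible.

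Whether SALT after prohibited treatment belongs in the primary analysis is an estimand choice on which statisticians may differ, since it counts hair changes under other therapies.

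**Conclusion.** The point holds in limited form. Following the plan as written can leave randomised patients without an observed Week 24 SALT for post-randomisation reasons, and the plan does not say how the primary MMRM handles them. Loss may differ by arm. Neither its size nor its direction follows from the documents. The 2 units of Step 3 bound one scenario and do not estimate the bias: they rest on 10% stopping, full return to the placebo level and no help from observed SALT. The placebo shifts of Step 4 rest on assumed values of k and D. The change is worth making because it is cheap and because data not collected at Week 24 cannot be recovered later.

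**What to change.** 1. Define stopping study drug and withdrawing from the study as separate events, with separate reasons. The rules on when drug is stopped stay as they are.
2. Remove protocol violation and non-compliance as grounds for withdrawal from the study.
3. Ask every randomised patient who stops drug before Week 24, unless consent is withdrawn, to attend the remaining scheduled visits, or at least Week 24, for SALT and a record of other treatments. Show this in Table 1.
4. Analyse by randomised group. State in advance whether SALT after stopping drug, and after prohibited treatment, enters the primary MMRM, and run the alternative as a sensitivity analysis. State the missing-data assumption and how an exit SALT maps to a scheduled visit.
5. Reconcile the Stopping Rules, since they determine who counts as having stopped. Any prohibited treatment is listed under permanent discontinuation, yet systemic corticosteroids and immunosuppressants, prohibited through exclusion criterion 14, also appear under temporary suspension.

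The cost is protocol wording and a few already-scheduled visits for roughly six patients (10% of 60), some of whom will decline. Off-drug or other-treatment values may move the estimate in either direction.

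### The Stopping Rules require a permanent stop for prohibited immunosuppressants, and the next list allows a temporary suspension for the same drugs

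*Combined protocol and SAP*

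**What the plan says.** The Stopping Rules consist of two lists, one after the other.

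- The first is mandatory: "Patients will be permanently discontinued from study treatment in the event of" a set of events that includes "Treatment with any prohibited concomitant medication or procedure". No exception is attached to that bullet.
- The second is optional: "Study drug dosing may be temporarily suspended in the event of" a set of events that includes "Treatment with systemic corticosteroids or non-steroidal immunosuppressive/immunomodulating medications (eg, cyclosporine, methotrexate, azathioprine, mycophenolate-mofetil, Janus kinase inhibitors, biologic agents, etc"). It closes with "Duration of study drug suspension should be reviewed on a case by case basis and can be discussed among the PIs".

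The Stopping Rules do not define what is prohibited. The Prohibited Treatment section does so by reference: "All treatments prohibited during the screening period are also prohibited throughout the course of the study". The reference leads to the Exclusion Criteria. Criterion 14 covers "Use of systemic immunosuppressive medications, including, but not limited to, cyclosporine, systemic or intralesional corticosteroids, mycophenolate mofetil, azathioprine, methotrexate, tacrolimus" and phototherapy, in the 4 weeks before randomization. Criterion 15 covers oral JAK inhibitors in the 12 weeks before Baseline.

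The Concomitant Treatment section opens other options only at the end of study dosing: "At Week 48, if subjects want to seek other treatment options (including commercially available dupilumab) for AA, they may do so".

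**The concern.** Read together, these sections give two instructions for one event. A patient who receives, for example, a systemic corticosteroid during treatment has taken a prohibited medication and must stop study drug for good. The same patient also meets the suspension bullet, under which dosing may be held and later resumed. Because suspension is worded as optional, continued dosing is a third possible reading.

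The trial runs at two sites, which could handle the same event differently. Before Week 24 the choice changes exposure to active drug only in the dupilumab arm. In a placebo patient it decides whether dupilumab is received in Phase II. The Analysis of Primary Endpoint section names an MMRM but does not say how data after prohibited medication or after stopping treatment are handled, so nothing in the stated analysis evens out such differences.

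**Working it through.** The plan states no figure on this point. The check is a comparison of text, followed by simple limits on exposure.

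**Step 1: which drugs fall under both rules.** Each agent or class in the suspension bullet is set against the prohibitions carried forward from the exclusion criteria. Screening takes place within 4 weeks of Baseline, so the 4-week and 12-week windows both cover it.

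| Agent or class in the suspension bullet | Named as prohibited? | Under both rules? |
|---|---|---|
| Systemic corticosteroids | Criterion 14 | Yes |
| Cyclosporine | Criterion 14 | Yes |
| Methotrexate | Criterion 14 | Yes |
| Azathioprine | Criterion 14 | Yes |
| Mycophenolate mofetil | Criterion 14 | Yes |
| JAK inhibitors (no route given) | Criterion 15, oral only | For oral use |
| Biologic agents | Not named | Unclear |

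Five overlap in full and one in part: 5 + 1 = 6 of 7. Whether the open-ended wording of criterion 14 also reaches biologics and non-oral JAK inhibitors cannot be settled from the text. The suspension bullet is itself an open list, so naming the drugs tells the reader more than the fraction does.

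**Step 2: is there anything that separates the rules?** The same section shows how two tiers are kept apart when that is intended:

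- Neutrophils: permanent stop at or below 0.5 x 10^3/µL; suspension at or below 1.0 but above 0.5.
- Platelets: permanent stop at or below 50 x 10^3/µL; suspension at or below 100 but above 50.

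Those tiers exclude each other. The two medication bullets have no boundary by dose, duration, route, indication or timing, and no statement of which takes precedence. The closing sentence on case-by-case review deals with how long a suspension lasts. It applies only once suspension has been chosen.

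**Step 3: when does the conflict operate?** From Week 0 to Week 48. After that there is no study dosing to stop or suspend.

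**Step 4: limits on exposure per affected patient.** The Study Design Overview gives Phase I = 24 − 0 = 24 weeks and Phase II = 48 − 24 = 24 weeks. Let the event occur at week k > 0 and a suspension last s weeks. After a permanent stop, 0 further dosing weeks remain. After suspension and resumption:

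- Event in Phase I: max(0, 24 − k − s) dosing weeks remain before Week 24, and all 24 weeks of Phase II if k + s ≤ 24.
- Event in Phase II: max(0, 48 − k − s) dosing weeks remain.

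The difference between the two rules, in weeks of active drug, is therefore:

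| Arm and time of event | Before Week 24 | Weeks 24 to 48 |
|---|---|---|
| Dupilumab, Phase I | less than 24 | up to 24 |
| Placebo, Phase I | 0 | up to 24 |
| Either arm, Phase II | none | less than 24 |

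As an illustration with assumed values, take k = 8 and s = 4. A dupilumab patient who resumes has 24 − 8 − 4 = 12 dosing weeks left before Week 24 and 24 in Phase II, 36 in all. Under a permanent stop the figure is 0. These are exposure limits only; no effect on SALT is assumed.

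**The case against.** The strongest reply is that a mandatory rule and a permissive rule do not strictly contradict each other. A site that always discontinues breaches neither. Suspension could be read as an interim hold before the mandatory rule takes effect, and the suspension bullet would still have work to do for agents not named as prohibited. All of this is fair, but the interim reading is nowhere stated, and a reader could equally let the more specific bullet govern. A site that resumes dosing after one of the six overlapping drugs follows the second list and breaches the first.

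A second reply is that the conflict has to be inferred: the exclusion criteria are washout windows, not a list of drugs forbidden on study. That is true, but the Prohibited Treatment section explicitly extends them. The lack of a single list of prohibited drugs is part of the cause.

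Third, oversight may catch divergence. Adverse events are reviewed monthly, the teams meet about every three months, and concomitant medications are recorded at every visit. This makes events traceable and undetected divergence less likely, but it supplies no rule for deciding a case.

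Finally, the week counts in the working restate the phase lengths and approach their maximum only for an event soon after dosing starts and a very short suspension. No effect on the Week 24 result has been shown. Both points stand. The case rests on two stated rules in conflict, not on a demonstrated bias.

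**Conclusion.** The inconsistency is real and lies in the current text. Systemic corticosteroids, cyclosporine, methotrexate, azathioprine, mycophenolate mofetil and oral JAK inhibitors each trigger a mandatory permanent stop and an optional temporary suspension, and nothing says which applies. Biologics and non-oral JAK inhibitors are unresolved.

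The conclusion rests on reading the screening prohibitions as exclusion criteria 14 and 15 carried forward, which is what the Prohibited Treatment section says. The possible consequence per affected patient is large in exposure terms, and before Week 24 it falls on the dupilumab arm alone. Its size at trial level is unknown, because the documents give no rate of use. The point should be corrected because the rules decide who stays on study drug on either side of the primary endpoint.

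**What to change.** Reconcile the Prohibited Treatment section, the permanent-discontinuation list and the temporary-suspension list so that exactly one rule applies to each case. If both rules are meant to remain, state what separates them or which takes precedence, with the same clarity as the neutrophil and platelet tiers. State whether biologic agents and non-oral JAK inhibitors count as prohibited; a single list of treatments prohibited on study would do this. Which clinical rule applies is for the sponsor to decide.

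The cost is close to nil: a wording clarification in three places, with no new data, visits or patients.
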